Exclusion Criteria: (a) diagnosis of organic brain disorder, bipolar disorder, schizophrenia, schizo-affective, schizophreniform, or paranoid disorder, (b) current suicidality, (c) evidence of neurocognitive dysfunction, (d) contraindications for tDCS (e.g seizure disorder), (e) probation/parole requirements or an upcoming move that might interfere with protocol participation, (f) planning to terminate buprenorphine or methadone in less than 3 months, and (g) scalp lesions near the tDCS electrode sites.

Exclusion Criteria related to FMRI scanning are: (a) history of neurological disorder (e.g., epilepsy, stroke, brain injury with loss of consciousness>10 min), (b) impaired uncorrected vision, and (c) MRI contraindications (e.g., claustrophobia, specific metallic implants and injuries, and pregnancy).

tDCS-related considerations: Careful consideration will be given when determining whether tDCS is safe for potential participants. Additional exclusion criteria related to tDCS include: metal implanted in the cranial cavity, pacemaker, poor cognitive functioning (i.e., Alzheimer's disease or dementia), history of neurological disorder (e.g., epilepsy or other seizure disorder), or other significant or chronic medical conditions that affect the brain (e.g., Parkinson's disease, Huntington's disease, multiple sclerosis, traumatic brain injury). [name] will have the final decision regarding whether a participant is medically stable enough to engage in this trial.

2.d Power Calculation and Sample Size:

In the UG3 phase of this project, we plan to enroll 60 participants. With an expected attrition rate of 20% (data loss over two sessions due to poor performance or movement artifact—a conservative estimate that is a larger loss than in our ongoing FIRST study), our final sample size will be 48, or 24 per group. This number provides 82% power for the expected effect size of .75, chosen based on prior tDCS studies and our belief that a large effect size should be required to continue to the UH3. In the UH3 phase, we again anticipate a 20% attrition rate over the 5 tDCS sessions and initial two fMRI scans. If the third scan (at 4 weeks) is missed, we expect this will be due to treatment drop-out or relapse. With 100 participants enrolled, we will have a final sample of 80 patients which provides a power of .8 to detect a group difference in relapse between relapse and sham of 15% vs 39% at 3 months follow-up.

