EEG Data Processing. Semi-automatic preprocessing for artifact detection will be performed using the FASTER algorithm (Nolan, Whelan, & Reilly, 2010). This EEGLAB toolbox uses Welch methods and removes muscle, heart, motion, ocular artifacts, and other noise using a multiple step procedure consisting of a) bandpass and notch filtering, b) Independent Component Analysis (ICA), c) rejection and/or interpolation of bad channels/epochs. The final step of preprocessing includes visual inspection of the data rejecting any remaining artifactual epochs. Windows of 1400 ms (1100 -2500 ms after stimulus onset) will be included in analysis. Theta band (4 -8 Hz) power in frontal (Afz, Fz) electrodes will be averaged across both n-back levels.

Working Memory and EEG Summary Indices. Working memory performance at each assessment will be represented by d' to capture executive skills without influence by demographic variables, psychiatric status, or intelligence quotient (Haatveit et al., 2010). For each participant, and within each n- condition, values for d' will thus be calculated by dividing the difference of Z (false alarms) and Z ("hits") by the root mean square of 2; d' captures the participant's ability to discriminate between the two stimulus types (i.e., the 2-back target letters and the non-target letters). Difference in theta power between 0-back and 2-back conditions (Δtheta) will also be calculated at EEG/n-back assessment. Comparison of pre- versus post-treatment Δtheta will test the primary hypothesis that opioid dependent participants who received the active tDCS intervention will show greater increases in theta power after 5 intervention sessions than sham tDCS recipients. Estimation of power spectrum density (PSD) values in the beta band (13-30 Hz) will be computed and averaged from channels in four regions (frontal, central, temporal, and occipital-parietal) for analysis in relation to craving scores.

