EEG outcome measures analyses. We will conduct a repeated-measures ANCOVA with a within-subject factor of time (baseline and end-of-stimulation (EOS)), between-subject factor of intervention condition (active tDCS and sham) and covariates to test if there is a statistically significant difference in in the EEG outcome (Δtheta) across treatment groups. Pearson correlations will be used to examine beta PSD values in relation to craving scores. A separate ANCOVA with the same factors will be used to explore treatment group differences in resting state EEG beta PSD values. Covariates for both analyses will include the baseline measure of the evaluated outcome, as well as baseline variables found to vary significantly ($p < 0.05$) by intervention arm, or which significantly ($p < 0.05$) predict attrition at EOS. Post-hoc t-tests will be used to probe anticipated significant interactions.

5. Quality Assurance

All research personnel, will have formal training in research with human subjects (e.g., CITI training, NIH Human Subjects training). Drs. [name], [name], and [name] will provide training to and supervise research assistants. Research assistants will also have training in Good Clinical Practice.

Drs. [name] and [name] will be responsible for quality control of this study. They will review recruitment and retention reports, and AE reports on a weekly basis. The MPIs (or their designee) will inspect BL documents (consent forms, release of information) for completeness within a week after they are signed. The MPIs (or their designee) will also conduct protocol and data quality monitoring twice a year using a checklist. This monitoring will include reviewing other study records to ensure completeness.

6. Regulatory Issues

6.a, 6.c Reporting of SAEs, Non-Medication Trials

Drs. [name] and [name] will be responsible for overseeing the daily safety of all participants. There are several ways in which they will become aware of adverse events. First, research staff will ask participants about serious adverse events (as defined by Office of Human Research Protections (OHRP); e.g., inpatient hospitalization) at each research contact point (UG3: baseline, week 2 assessment, 5 tDCS appointments, 2 fMRI; UH3: baseline,

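### The EEG repeated-measures ANCOVA uses baseline both as an outcome level and as a covariate, without naming a covariate-by-time term or the treatment test, so whether baseline is adjusted for depends on the fit.

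*Combined protocol and SAP*

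**What the plan says.** Section 4.c, under EEG outcome measures analyses, specifies a repeated-measures ANCOVA for Δtheta (the difference in theta power between the 0-back and 2-back conditions). It has a "within-subject factor of time (baseline and end-of-stimulation (EOS" and a "between-subject factor of intervention condition (active tDCS and sham". A separate ANCOVA with the same factors explores resting beta power. The covariate rule is common to the two: "Covariates for both analyses will include the baseline measure of the evaluated outcome". It then adds baseline variables that differ by arm at p < 0.05 or that predict attrition at EOS at that level. The follow-up is: "Post-hoc t-tests will be used to probe anticipated significant interactions".

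The preceding paragraph on EEG summary indices implies that treatment is judged by the change over time: "Comparison of pre- versus post-treatment Δtheta will test the primary hypothesis".

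The section does not say whether each covariate is crossed with time, whether the fit is a classical general linear model or a mixed model, what covariance structure applies, or which term is the treatment test.

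**The concern.** A baseline value that is already one of the two outcome measurements cannot also serve as an ordinary main-effect covariate and adjust the treatment contrast. What the covariate does depends on a term the plan does not mention. With that term, the analysis is baseline-adjusted ANCOVA. Without it, the plan appears to adjust for baseline but does not, and it loses the precision that the adjustment was presumably meant to bring.

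The reported effect is also left open. The adjusted interaction, the unadjusted interaction and the arm main effect are different numbers, and section 2.a, 2.b expects the UG3 phase to yield an effect size. The post-hoc t-tests, as described, carry no baseline adjustment, so they need not agree with an adjusted main test.

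**Working it through.** **Inputs.** From section 2.d: "our final sample size will be 48, or 24 per group", and "This number provides 82% power for the expected effect size of .75". That section does not tie the 0.75 to the EEG outcome; here it is taken in SD units of the EOS value. The baseline-EOS correlation ρ is not in the documents, so 0.3, 0.5 and 0.7 are assumed. Alpha for the treatment test is not stated; two-sided 0.05 is assumed.

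**The plan's own figure.** A two-sample t-test with 24 per arm has noncentrality 0.75 × √(24/2) = 2.598 on 46 df. Power is 82.0% at one-sided 0.05 and 72.0% at two-sided 0.05. The stated 82% therefore matches a one-sided test. No power is stated for the EEG ANCOVA itself.

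**Algebra.** Let Y be the outcome, B its baseline value, g the arm (0/1) and t the time (0 = baseline, 1 = EOS).

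- Baseline as main effect only: Y = a + b·t + c·g + d·g·t + e·B. Subtracting the two rows of one participant gives Y₁ − Y₀ = b + d·g + error. B has cancelled, so the test of d is the t-test on change scores.
- With covariate-by-time, f·B·t is added and Y₁ − Y₀ = b + d·g + f·B + error. Since Y₀ = B, this is Y₁ = b + d·g + (1 + f)·B + error, which is ANCOVA of EOS on arm and baseline.

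**Check on one simulated data set.**

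| Fit | Estimate | SE | p |
|---|---|---|---|
| ANCOVA of EOS on arm + baseline | 0.4678 | 0.2187 | 0.0379 |
| Arm-by-time, covariate × time included | 0.4678 | 0.2187 | 0.0379 |
| Arm main effect, same model | 0.2339 | 0.1093 | 0.0379 |
| Arm-by-time, covariate × time omitted (change score) | 0.6634 | 0.2510 | 0.0112 |

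The first two rows are identical. The arm main effect is exactly half of them. The last row is a different estimate.

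**Power.** With unit variance at each time, the SD of change is √(2(1 − ρ)) and the ANCOVA residual SD is √(1 − ρ²). Noncentrality is 0.75 × √12 divided by that SD, on 46 and 45 df respectively. The ANCOVA formula ignores chance baseline imbalance, so it runs slightly high.

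| ρ | SD of change | Noncentrality | Power, change score | Residual SD, ANCOVA | Noncentrality | Power, ANCOVA |
|---|---|---|---|---|---|---|
| 0.3 | 1.183 | 2.196 | 57.5% | 0.954 | 2.724 | 76.0% |
| 0.5 | 1.000 | 2.598 | 72.0% | 0.866 | 3.000 | 83.5% |
| 0.7 | 0.775 | 3.354 | 90.7% | 0.714 | 3.638 | 94.5% |

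Simulations gave 56-58% against 73-76%, 72-74% against 82-85%, and 90-91% against 94%. At ρ = 0.9 both are about 100%. The variance ratio, ANCOVA to change score, is (1 − ρ²)/(2(1 − ρ)) = (1 + ρ)/2, or 0.65, 0.75 and 0.85 at the three correlations.

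**Type I error** (20,000 null runs, ρ from 0.3 to 0.9). ANCOVA, and equally the model with covariate × time: 4.8-5.1%. Change score: 4.9-5.2%. Both are valid. Only a mixed model with a random intercept and baseline as a main effect departs from this. Its two residuals are negatively correlated, the intercept variance goes to zero, and in the example the SE falls to 0.233 from 0.251. Type I error is then 7.8%, 6.9%, 6.3% and 5.4% at ρ = 0.3, 0.5, 0.7 and 0.9.

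**The case against.** The strongest reply is that a classical repeated-measures ANCOVA fitted as a general linear model crosses covariates with time. The arm-by-time test is then exactly ANCOVA, and the proposed change alters no result. This stands, and it limits the point to one of specification. It does not remove it, because the plan does not say that this is the fit.

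A reader might go further and infer that the double use of baseline must either remove the adjustment or inflate the error rate. The documents do not support that. The either/or omits the covariate-by-time fit, which is fully adjusted and valid. The inflation needs a random-intercept mixed model, or stacked rows treated as independent, and the plan names neither. For a within-subject analysis with two time points and subject-level error, the test holds its level.

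A reader might also infer that the go/no-go decision is compromised. Under sections 2.a, 2.b and 8.a, enhanced frontal theta is an alternative to fMRI change in any craving or cognitive-control node, and a greater change in craving is required as well. No p-value threshold is set for theta. The beta analysis is exploratory.

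Finally, the loss of power depends on a correlation that the documents do not give, and at 0.7 it is only about 3 to 4 points.

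**Conclusion.** The specification is redundant and incomplete, and nothing elsewhere in the documents settles it. Taken as listed, the baseline covariate does nothing for the arm-by-time test. The cost is power: roughly 15 to 18 points at an assumed correlation of 0.3, about 11 at 0.5 and 3 to 4 at 0.7, with no loss of validity. With covariate-by-time there is no cost. These figures assume 24 per arm, two-sided 0.05, equal variances at the two times, and an effect of 0.75 SD of the EOS value.

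The point is worth correcting but modest. It concerns a UG3 validation measure and an exploratory one; the UH3 comparison of relapse at 3 months is a separate chi-square test and is unaffected.

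**What to change.** Replace the repeated-measures wording with a direct statement: EOS Δtheta will be compared between arms by ANCOVA, with baseline Δtheta as a covariate together with the other covariates the plan already lists (baseline variables that differ by arm or predict attrition at EOS). The adjusted arm difference, with its confidence interval, is both the treatment test and the reported estimate. Specify resting beta power in the same way. Drop the unadjusted post-hoc t-tests, which add nothing to a contrast of two arms at two times.

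If the team prefers to keep the time factor, it should state that every covariate is crossed with time and that arm-by-time is the test; for complete pairs the result is the same. In either case, state alpha and sidedness.

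The cost is a few lines of analysis-plan text. No data collection or sample size changes, and if the covariate-by-time fit was intended, the arm-by-time result does not change either.

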Grant Number: UH3DA047793

Title: tDCS to Decrease Opioid Relapse

MPIs: [name] and [name]

Medical Monitor: [name]

2. Summary of the Protocol:

2.a, 2.b Brief Description of the Protocol, Primary and Secondary Outcome Measures

This study has two phases. In phase one (UG3), we propose to use functional magnetic resonance imaging (fMRI) and electroencephalographic (EEG) to quantify changes in brain function and reported craving before and after administration of five sessions of transcranial direct current stimulation (tDCS) targeting the right dorsolateral prefrontal cortex (DLPFC). Opioid dependent participants (n=60) who recently initiated buprenorphine or methadone will be randomized to tDCS+Cognitive Control Network (CCN) priming stimulation vs. sham tDCS+CCN priming. Participants in their first month of prescribed buprenorphine or methadone will be assessed using fMRI and EEG, once prior to tDCS and again one week later after completion of 5 sessions of tDCS+CCN priming. With a focus on the craving outcome, we will use two task-based fMRI paradigms that challenge networks associated with craving (CR) and cognitive control (CCN), and will examine these and the salience network using resting state functional connectivity. We examine an additional validation measure of the effect of tDCS on the DLPFC – an oscillatory target -- EEG frontal theta power during working memory(WM). In this UG3 phase, fMRI and EEG will be expected to provide 1) validation of expected network and oscillatory changes from tDCS-targeting and 2) an effect size for DLPFC vs sham stimulation. Go/no go criteria for the UG3 phase will be demonstration of greater fMRI change in any node of the CR or CCN networks or enhanced frontal theta power during a WM task AND greater change (at least 10% difference between conditions, controlling for baseline craving) in subjective craving measured during a cue reactivity task or outside the fMRI following the tDCS+CCN priming intervention compared to sham tDCS+CCN priming.

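### Beyond the baseline outcome, the EEG covariates are chosen by p<0.05 screens rather than prespecified, which costs precision and leaves the covariate list open until arm codes are seen

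*Combined protocol and SAP*

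**What the plan says.** The EEG text of section 4.c sets out the model: "We will conduct a repeated-measures ANCOVA with a within-subject factor of time" (baseline and end of stimulation), intervention arm as the between-subject factor, and covariates. A separate ANCOVA with the same factors covers resting beta power.

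The covariate rule has a fixed part and a screened part. The fixed part is unconditional: "Covariates for both analyses will include the baseline measure of the evaluated outcome". The screened part adds "baseline variables found to vary significantly" by arm at p<0.05, "or which significantly ($p < 0.05$) predict attrition at EOS". The plan gives no candidate list, does not name the tests, sets no cap on the number of covariates, and does not make association with the outcome a criterion.

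The outcome concerned is the change in theta between memory loads: "Comparison of pre- versus post-treatment Δtheta will test the primary hypothesis" of the EEG component. The comparison is randomised; UG3 participants "will be randomized to tDCS+Cognitive Control Network (CCN) priming stimulation vs. sham tDCS+CCN priming" (sections 2.a, 2.b). Frontal theta is also one of the alternatives in the neural half of the UG3 go/no-go criteria (sections 2.a, 2.b and 8.a).

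The last sentence of the fMRI analysis text in section 4.c fixes substance use type as a model covariate. It stands just before the EEG heading, so whether it also governs the EEG models is unclear.

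**The concern.** A covariate earns its place by predicting the outcome. A test of baseline difference between randomised arms does not measure that. If randomisation was carried out properly, any difference found is chance, so the screen passes a strong predictor and an irrelevant variable at the same rate.

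Three things follow for a team that applies the rule exactly as written. A predictor that would sharpen the comparison is left out in most trials. A variable may be adjusted for only because it happened to differ. And the final covariate list cannot be written down until arm codes have been used to test for imbalance. With no candidate list, the choice of which variables to test also rests with the analyst. At stake are precision and prespecification in a comparison expected to have 24 analysed per group.

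**Working it through.** **Inputs from the documents.** Section 2.d: 60 enrolled, 20% attrition, 48 analysed (24 per group), effect size 0.75, power 82%. Section 4.c: both screens at p<0.05, baseline outcome always included. The number of candidates and all correlations are assumptions, because the plan gives neither.

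**The plan's own figure.** 60 × 0.80 = 48. For a two-sample t-test the noncentrality is 0.75 × √(24/2) = 2.598 on 46 df. Power is 82.0% one-sided at 5%, which reproduces the stated figure, and 72.0% two-sided. The plan states neither alpha nor sidedness. The calculations below use two-sided 5%.

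**Chance of selection, one variable.** The arm screen selects at rate 0.05 whatever the variable's prognostic strength. For a variable unrelated to dropout, treating the two tests as independent, either route admits it with probability 1 − 0.95² = 9.75%.

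**Chance that at least one of k variables enters by luck.** The formula is 1 − 0.95^k for the arm test and 1 − 0.95^(2k) for both tests, with independent candidates.

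| k (assumed) | Arm test only | Both tests |
|---|---|---|
| 5 | 23% | 40% |
| 10 | 40% | 64% |
| 20 | 64% | 87% |

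**The attrition screen when a real association exists.** Take 12 lost and 48 retained, using the section 2.d rate as a stand-in for EEG attrition. Noncentrality is d × √(12 × 48/60) = 3.098d on 58 df. Selection probability is 9%, 33% and 68% for standardised differences of 0.2, 0.5 and 0.8. This route is therefore not pure chance, although it is weak unless the association is strong.

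**Effect on power.** Simulation of 8,000 trials per row, 24 per arm, effect 0.75 SD, ANCOVA on the end-of-stimulation value with the baseline outcome always in the model. One further predictor, uncorrelated with baseline, either enters only if its arm test has p<0.05 or is prespecified. The attrition route is not simulated.

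| r, baseline | r, further predictor | Screened | Prespecified | Gain (points) |
|---|---|---|---|---|
| 0.3 | 0.3 | 75.3% | 78.2% | 2.9 |
| 0.3 | 0.5 | 75.7% | 86.6% | 10.9 |
| 0.5 | 0.3 | 83.0% | 86.4% | 3.4 |
| 0.5 | 0.5 | 83.8% | 94.1% | 10.3 |
| 0.7 | 0.3 | 94.7% | 97.0% | 2.3 |
| 0.7 | 0.5 | 95.2% | 99.9% | 4.7 |

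Simulation error on a power near 80% is √(0.8 × 0.2/8000), about 0.4 points.

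A hand check on the fourth row: with baseline alone the noncentrality is 2.598/√(1 − 0.25) = 3.00, and with both covariates 2.598/√(1 − 0.50) = 3.67. These give about 84% and 95%, close to the simulation.

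**When the further predictor overlaps with baseline** (correlation 0.3 or 0.5 between them, baseline r of 0.5 or 0.7, 6,000 trials), the gain shrinks. It is about −0.7 to +0.1 points for a predictor with r = 0.3, which is effectively nothing, and about 1 to 5 points for one with r = 0.5.

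**Type I error under the screen**, uncorrelated scenarios: 3.7% to 4.8% against a nominal 5%.

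**The case against.** The strongest reply is that the most valuable covariate is already in the model. The baseline value of the outcome is plausibly its strongest single predictor, and it enters without any screen. A reader who starts from the screened half of the sentence might infer that strong predictors are almost never adjusted for, or that chance decides the model. The documents do not support either: time, arm and the baseline outcome are all fixed. A power comparison that leaves the baseline outcome out gives losses such as 71% against 82% (r = 0.5) or 74% against 94% (r = 0.7), but that is not the model in the plan. This objection stands, and it limits the point to covariates beyond the baseline outcome.

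Second, the attrition route is defensible in principle. The variables adjusted for are all measured at baseline, dropout only guides which are chosen, and conditioning on predictors of dropout can make a missing-at-random assumption more plausible. It needs no arm codes, so the unblinding point applies to the arm screen alone. Also, baseline differences are purely chance in the full randomised set but not necessarily among completers, and the plan does not say which set is tested. This largely stands. What remains is that a p<0.05 screen with about 12 dropouts is a weak way to find such variables.

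Third, a reader might infer false-positive findings or a compromised go decision. The simulated type I error is at or slightly below 5%. Theta is one alternative beside fMRI change in any node of two networks, and a craving difference is required as well. No text ties the go decision to the p-value of this ANCOVA. None of this, however, repairs the imbalance screen.

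**Conclusion.** The concern holds for the covariates added to the baseline outcome. The arm screen ignores prognostic value, leaves the list unspecified until arm codes are used, and usually gives a less precise analysis than a short fixed list would.

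The loss is modest: about 0 to 4 power points for a further predictor correlated 0.3 with the outcome and about 1 to 11 for one correlated 0.5, with the smaller values when it overlaps with the baseline value. The cost is precision and analyst discretion, not a raised false-positive rate.

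These sizes rest on assumed correlations and candidate counts, independent candidates, a two-sided 5% test and an ANCOVA on the end-of-stimulation value. The point touches the EEG hypothesis and one alternative in the UG3 go/no-go. It does not touch the UH3 relapse comparison, which section 4.c assigns to a Pearson chi-square test. The rule should be changed, but the trial's main clinical conclusion does not depend on it.

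**What to change.** In the EEG text of section 4.c, remove the p<0.05 imbalance screen. Prespecify the covariates as the baseline outcome plus at most one or two named baseline variables chosen for expected prognostic value. State whether substance use type, fixed in the fMRI text, applies to the EEG models. Medication at entry (buprenorphine or methadone) is another variable already known, but nothing in the documents shows that either one predicts the theta outcome, so the team should justify its choice. Put baseline predictors of attrition in a prespecified missing-data sensitivity analysis, or name them in advance.

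This takes a sentence or two in the plan, made before arm codes are seen, with no new data and no participant burden. The downside is small: a named covariate that proves non-prognostic costs about one degree of freedom out of roughly 45.
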